2 SYNOPSIS

Title	An observational case control study of the use of siltuximab (SYLVANT) in patients diagnosed with COVID-19 infection who have developed serious respiratory complications
Developmental Phase	This is an observational case control study.
Institution	Azienda Socio-Sanitaria Territoriale Papa Giovanni XXIII, Bergamo, Italy
Study Centers	1 study center
Background	This observational study will collect data from patients treated under this already approved compassionate use program. The compassionate use programme was for treatment with SYLVANT siltuximab 400mg in patients diagnosed with COVID-19 infection who have developed serious respiratory complications.
	This observational study will group the patients into two cohorts receiving siltuximab. Patients in Cohort A are treated in a non-ICU setting and patients in Cohort B are in an ICU setting.
	Each patient will have a matched case control receiving standard treatment without siltuximab.
Objectives and	Primary objective
Endpoints	Cohort A: reduction of the need of invasive ventilation or 30-day mortality
	Cohort B: reduction of mortality
	Secondary objectives
	Cohort A
	Reduction of the need of time of ventilatory support
	Improvement of the lung function
	Improvement of radiologic findings
	Cohort B
	Reduction of days of need of intubation
	Percentage of patients that undergo to tracheostomy
	Improvement of the lung function
	Improvement of radiologic findings
	Primary endpoint:
	Cohort A: Reduction of the rate of need of invasive ventilation or 30-day mortality
	Cohort B: Reduction of length of ICU staying or 30-day mortality
	Secondary endpoints:
	Cohort A
	Reduction of days of need of ventilatory support
	Improvement of P/F fraction (resolution of ARDS i.e. P/F>300, or increase from baseline value of at least 50% if P/F>100 or 100% if P/F<100, at day 3, 8 and 15)

Reduction of the duration of invasive ventilation or length of ICU

Improvement of radiologic imaging

Cohort B

Reduction of days of need of intubation

Percentage of patients that undergo tracheostomy

Improvement of P/F fraction (resolution of ARDS i.e. P/F>300, or increase from baseline value of at least 50% if P/F>100 or 100% if P/F<100, at day 3, 8 and 15)

Improvement of radiologic imaging

• Exploratory end points

Correlation of outcomes with IL-6 levels

Study Design

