This is a single-center observational case control study in Italy that follows the use of treatment with siltuximab in patients with COVID-19 who have developed serious respiratory complications. Retrospective data collection will be carried out on those patients who have received the drug through the compassionate use program (this program is still ongoing, and enrolling patients).

Patients receiving siltuximab that will be included into this observational study will be divided into 2 cohorts, and per current estimation split in a 3:1 ratio: 75% will be in Cohort A as not treated in an ICU setting and are not on mechanical ventilation, while 25% will form Cohort B and consists of patients in an ICU setting who are receiving invasive ventilation.

Each patient will be matched to a consented case control patient receiving treatment other than siltuximab for their condition.

Match Criteria

Patients and controls will be matched according to the following criteria:

- Age (by decades)
- Sex (M/F)
- P/F fraction (<100, 100-150 or >150) at baseline
- Antiviral therapy

Procedures outlined in this protocol are based on the compassionate use program, where patients are managed as per clinicians' best judgement and best practice. No clinical procedures are required by this observational protocol. Data on the procedures already performed during the routine diagnosis and treatment of COVID-19 patients will be collected. The list of clinical and laboratory parameters is provided to direct data collection for this observational study (as available in the medical records).

During their hospitalization, patients will be monitored as per standard hospital practice or as per national (emergency) guidelines in accordance with extraordinary circumstances relating to the COVID-19 outbreak. After discharge, patients will be asked to provide (from their primary health care providers) relevant laboratory results for 30 days following start of COVID-19 treatment via ventilation (either mechanical or non-invasive).

Data Collected

Data collection for this study will be on the basis of existing medical records i.e. from standard practice tests at the hospital. The following data will be collected /recorded (if available):

• Laboratory-confirmed COVID-19 test and date of diagnosis;

- Other medical history;
- Concomitant medications.

The following data will be recorded from the time of first ventilation for 30 days (if available):

- General information:

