5 INTRODUCTION

Coronaviruses (CoV) are a large family of viruses that cause illness ranging from the common cold to more severe diseases such as Middle East Respiratory Syndrome (MERS-CoV) and Severe Acute Respiratory Syndrome (SARS-CoV). A novel coronavirus (nCoV) is a new strain that has not been previously identified in humans (WHO).

One of the most serious potential symptoms that can occur with a coronavirus is the so-called 'cytokine storm' – when the immune system becomes over-stimulated and begins to attack a patient's own body. It has already been recognized that potential symptomatic treatment of critically ill COVID-19 infected patients should be directed towards reducing excessive immune response (A. Zumla, DS Hui et al.)

Medics already have considerable experience managing cytokine storms and excessive immune reaction with IL-6 blockers like tocilizumab. Roche has secured approval from China for its anti-inflammation drug Actemra (tocilizumab) to treat patients developing severe complications from coronavirus (COVID-19). In its latest treatment guidelines published online, the commission said that the biologic drug Actemra can now be used to treat coronavirus patients with severe lung damage and high IL-6 levels (Pharmaceutical-technology.com).

SYLVANT® (siltuximab) is a monoclonal antibody that prevents IL-6 from binding to IL-6 receptors and therefore causes blockade of IL-6 (EUSA Pharma UK).

In the Compassionate Use Program, critically ill COVID-19 patients (with a confirmed diagnosis) with severe acute respiratory distress will be treated with a single intravenous infusion of siltuximab (SYLVANT), Blocking of the excessive IL-6 could diminish the excessive immune response and consequently reduce its toxic effect on lungs. Early control of excessive immune response in acute respiratory distress syndrome may reduce mortality and might also ensure faster recovery with milder consequences.

This observational case control study will collect and analyze the data from patients who were treated under the compassionate use program (still ongoing). This study will assess the treatment effects of siltuximab in diagnosed COVID-19 patients with serious respiratory complications and could provide valuable insight into the development of treatments for patients with COVID-19.

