5.1 Study Rationale

There is an emergency situation regarding treating patients with COVID-19 and especially those with lung complications and/or acute respiratory distress syndrome (ARDS), which is the main cause of morbidity and mortality in these patients. Siltuximab (SYLVANT) 400 mg is an approved product and dosage for idiopathic Multicentric Castleman Disease (iMCD): it is not indicated for the treatment of COVID-19 infection. However, due to observed clinical (lung dysfunction) and laboratory (high IL-6) presentation in COVID-19 patients, siltuximab (an IL-6 blocker) may potentially benefit patients who developed respiratory complication.

As siltuximab is being used for the first time in this indication, there is a requirement to collect and analyze efficacy and safety data from both the standard of care and siltuximab

treated patients in order to assess risk/benefit as well as the dosing regimen of siltuximab in this patient population. As this is an observational case control study, only available data will be collected and analyzed.

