8 OBSERVATIONAL PLAN

8.1 Overall Study Design and Plan – Description

This is a single-center, observational case control study in Italy that follows the use of treatment siltuximab in patients diagnosed with COVID-19 infection who have developed serious respiratory complications. Retrospective data collection will be carried out on patients who have received the drug through the compassionate use program. (this program is still ongoing, and enrolling patients).

Patients receiving siltuximab will be included into this observational study and will be divided into 2 cohorts, split in an approximate 3:1 ratio: 75% will be in Cohort A and are not in an ICU setting and are not on mechanical ventilation, while 25% will form Cohort B and consists of patients in an ICU setting who are receiving invasive ventilation.

[figure not shown]
Each patient will be matched to a consented case control receiving treatment other than siltuximab for their condition.

Match Criteria

Patients receiving siltuximab and controls will be matched according to the following criteria:

- Age (by decades)
- Sex (M/F)
- P/F fraction (<100, 100-150 or >150) at baseline
- Antiviral therapy

Figure 1: Study Design

Procedures outlined in this protocol are based on the compassionate use program, where patients are managed as per clinicians' best judgement and best practice. No procedures are required by this observational protocol. Data on the procedures already performed during the routine diagnosis and treatment of COVID-19 patients will be collected. The list of clinical and laboratory parameters is provided to direct data collection for this observational study (as available in the medical records).

During their hospitalization, patients will be monitored as per standard hospital practice or as per national (emergency) guidelines in accordance with extraordinary circumstances relating to the COVID-19 outbreak. After discharge, patients will be asked to provide (from their primary health care providers) relevant laboratory results for 30 days following start of COVID-19 treatment via ventilation (either mechanical or non-invasive).

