9.1.2 Exclusion Criteria

Patients who meet the following criteria may NOT participate in the study.

1. Active infection of bacterial or viral (non-Covid-19) origin

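### The control group is defined in two ways, and no rule says whether a control may have received another IL-6 blocker

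*Protocol*

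**What the plan says.** The protocol describes the comparator in four places, with two scopes.

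- Section 2, Background: "Each patient will have a matched case control receiving standard treatment without siltuximab".
- Section 5.1 gives the need to "collect and analyze efficacy and safety data from both the standard of care and siltuximab" treated patients, so here too the comparator is standard of care.
- Section 2, Study Design: "Each patient will be matched to a consented case control patient receiving treatment other than siltuximab for their condition".
- Section 8.1 repeats the broader wording: "Each patient will be matched to a consented case control receiving treatment other than siltuximab for their condition".

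The only exclusion criterion (9.1.2) is "Active infection of bacterial or viral (non-Covid-19) origin". None of the inclusion criteria in 9.1.1 restricts other treatment. Of the four match factors in 8.1, the only one that concerns treatment is "Antiviral therapy". Section 5 says: "Medics already have considerable experience managing cytokine storms and excessive immune reaction with IL-6 blockers like tocilizumab". It then reports that tocilizumab was approved in China for severe COVID-19 complications, and it describes siltuximab as blocking IL-6 as well. Section 8.2 says the controls are there so that the groups can be compared directly. Section 11 plans that comparison descriptively, within each cohort.

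**The concern.** The two wordings do not cover the same patients. Standard care is a restricted set of treatments, even if it is left undefined. The wording in 8.1 takes in every treatment except one drug. The protocol itself names another drug that acts on the same pathway, and nothing in its eligibility or matching rules keeps that drug out of the control group. Background therapy was thought important enough to match on, but only for antivirals.

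What is at stake is the meaning of the one contrast that the control group exists to provide. With no formal test planned, readers will rely on the raw difference. If some controls had IL-6 blockade, that difference answers a mixed question, partly siltuximab against standard care and partly one IL-6 blocker against another. The safety contrast would be affected in the same way, because effects of the class could appear in both groups.

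**Working it through.** The protocol gives no figure to reproduce on this point: section 11.1 states no sample size calculation, and no event rate or effect is assumed anywhere. The check therefore has a textual part and an illustration on assumed values.

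**Text.** Could a patient who received tocilizumab and no siltuximab be a control?

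1. Section 8.1 and the synopsis Study Design: yes, because the treatment is not siltuximab.
2. Synopsis Background and section 5.1: undetermined, because standard treatment is not defined and might include such a drug.
3. Sections 9.1.1 and 9.1.2: nothing removes the patient.
4. Match factors: nothing prevents the pairing, provided age decade, sex, P/F band and antiviral therapy agree.

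Such a control is not excluded. Choosing the narrower wording without defining it would not settle the question.

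**Numbers of patients.** Up to 50 patients, half of them treated, gives 25 pairs. The estimated 3:1 split gives 0.75 x 25 = 18.75, about 19 pairs in Cohort A, and 0.25 x 25 = 6.25, about 6 pairs in Cohort B. One control is then 1/19 = 5% of Cohort A's controls and 1/6 = 17% of Cohort B's.

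**Illustration (all values assumed).** Let pc be the event risk under standard care, pt the risk under siltuximab, and D = pc - pt. A share f of controls receives another IL-6 blocker with effect r*D, and these controls are otherwise like the rest. Then

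- control risk = pc - f*r*D
- observed contrast = pc - f*r*D - pt = (1 - f*r)*D

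With pc = 50% and pt = 30%, D = 20 points. Share of the contrast kept, and observed difference:

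| f | r = 1 | r = 0.5 | r = 0 |
|---|---|---|---|
| 10% | 90%, 18 points | 95%, 19 points | 100%, 20 points |
| 25% | 75%, 15 points | 87.5%, 17.5 points | 100%, 20 points |
| 50% | 50%, 10 points | 75%, 15 points | 100%, 20 points |

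**If the drug goes to sicker patients.** Suppose these controls would have had risk pc + d without it. The observed contrast becomes (1 - f*r)*D + f*d. At f = 25%, r = 0.5 and D = 20 points, d = 10 gives 17.5 + 2.5 = 20 points, so the two effects cancel. At d = 20 it is 17.5 + 5 = 22.5 points, an exaggeration. The direction is not fixed.

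**Scale against chance.** Ignoring the matching, the 95% half-width of a risk difference with risk p in both groups is 1.96*sqrt(2p(1-p)/n). For p = 0.3 to 0.5 it is 29 to 32 points at n = 19 and 52 to 57 points at n = 6. The shifts in the table, 0 to 10 points, are well inside that.

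**The case against.** The two wordings can both be true of the same patient, and section 13.1 places all observed treatments within the attending physician's regular practice. On that view this is loose drafting rather than contradiction. That stands in part: the central gap is that the comparator is silent on other immunomodulators, and the mismatch in wording exposes it.

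A reader might infer from section 5 that controls at this centre were on tocilizumab and that the contrast is therefore diluted. The document does not support this. The sentence on experience with IL-6 blockers concerns cytokine storms in general, and the COVID-19 statements concern approval and guidelines in China. Nothing describes practice at the single Italian site. A reader might also infer that earlier tocilizumab in siltuximab patients would bias the comparison the opposite way. That does not follow either: patients given siltuximab after another drug had failed might do worse, which would also shrink an apparent benefit.

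The study is hypothesis-generating (8.2), and section 11.2.3 rules out statistical comparison of the groups, so no error rate is affected. COVID-19 treatments are recorded with start and stop dates (10.1.7), treatment information is to be presented (11.2.2) and there are patient-level listings (11.2), so affected controls could be found afterwards. All of this stands and limits the consequence. It does not supply a rule for who may be a control, and that belongs in the protocol, before controls are picked from existing records.

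Finally, siltuximab against whatever non-siltuximab care was given is a legitimate observational question. It is not the one that the synopsis background and section 5.1 pose, and the protocol would have to say so.

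**Conclusion.** The point holds as a defect of definition. The comparator has two scopes, the narrower one is undefined, and no rule excludes controls on another IL-6 or IL-6-receptor blocker. That such controls exist, or that dilution occurs, is not shown. The possible size depends on two quantities that the protocol does not give: at 25% use, 75% of the true contrast is kept if the other drug is equally effective, 87.5% if half as effective, and all of it if it has no effect. These figures also assume that the affected controls resemble the others; selective use in sicker patients could offset or reverse the distortion. The harm is to the interpretation of a small descriptive comparison, not to a powered test. The definition is still worth settling, because the contrast is the reason for having controls.

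**What to change.** Use one control definition in the synopsis (Background and Study Design), section 5.1 and section 8.1: standard care, with no IL-6 or IL-6-receptor blocker before or at the index time.

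- **Index time.** The protocol sets none for controls. Define it as the same elapsed time since the start of ventilation as the matched patient's siltuximab infusion.
- **Symmetry.** Apply the same prior-use rule to the siltuximab group, for drugs of this class other than the index infusion.
- **Later use.** Keep patients who receive such a drug after the index time in their group, tabulate it by group, and show the descriptive comparison with and without the affected pairs. Dropping whole pairs preserves the matching. The version without them selects on a later event, so it is supportive only.

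The cost is a somewhat smaller pool of eligible controls and a wording change in four places. The treatments are already collected under 10.1.7, but as dates. Because eligibility uses a 48-hour window, drugs started on the index day need a clock time from the record or a stated same-day rule.

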9 STUDY POPULATIONS

9.1 Eligibility

9.1.1 Inclusion Criteria

Patients must meet the following criteria to be eligible to participate in the study:

- 1. Clinical and radiological diagnosis of pulmonary infection by COVID-19
- 2. Positive microbiological evidence of SARS-CoV-2 infection
- 3. Diagnosis of acute respiratory distress syndrome clinical panel in accordance with Berlin 2012 criteria
- 4. For Cohort A only: subjects are eligible if they are enrolled and treated within 48 hours from the beginning of NIV or CPAP
- 5. For Cohort B only: subjects are eligible if they are enrolled and treated within 48 hours from the beginning of invasive ventilation

While approving this protocol, it is understood that the RA/IEC have approved collection and analysis of the data from deceased patients with COVID-19. See also protocol section 10.1.2.

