10.1.5 Medical History and Concomitant Diseases

Medical history findings (i.e., previous diagnoses, diseases, surgeries, and conditions) meeting all criteria listed below will be collected:

- Not pertaining to the study indication
- Considered relevant to the study

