11.1 Sample Size Determination

No statistical sample size estimation was performed. For this study patients from one single center in Italy will be enrolled as follows:

- All patients treated with siltuximab diagnosed with COVID-19 infection who have developed serious respiratory complications, and
- An equal number of case control patients that consented to their data collection.

It is estimated that in total up to 50 patients will be enrolled.

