13 ETHICAL AND LEGAL ASPECTS

13.1 Independent Ethics Committee or Institutional Review Board

No additional investigations, above those specified in the compassionate use program and the standard of care, will be performed. In addition, patients will not be systematically allocated to treatments. All treatments observed in this study have been prescribed for an indication within the regular practice of the attending physician, independent of his/her participation in this study (non-interventional).

In Italy, where review by an Independent Ethics Committee (IEC) is required, documented approval from appropriate IEC will be obtained from the participating site prior to study start, according to local laws, regulations and organizations.

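### Controls need not have been candidates for siltuximab, and the reason they did not receive it is not recorded, so the group contrast is open to confounding by indication in either direction

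*Protocol*

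**What the plan says.** **Who is a control.** Section 8.1 (and the Synopsis in near-identical words) says: "Each patient will be matched to a consented case control receiving treatment other than siltuximab for their condition". Section 11.1 adds only number and consent: "An equal number of case control patients that consented to their data collection".

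**Eligibility.** Section 9.1.1 opens with "Patients must meet the following criteria to be eligible to participate in the study", so its criteria bind controls too: COVID-19 lung infection, a positive test, ARDS by the Berlin definition, and a 48-hour window from the start of NIV/CPAP (Cohort A) or invasive ventilation (Cohort B). The one exclusion, in section 9.1.2, is "Active infection of bacterial or viral (non-Covid-19) origin".

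**Matching.** "Patients receiving siltuximab and controls will be matched according to the following criteria": age by decade, sex, "P/F fraction (<100, 100-150 or >150) at baseline", and antiviral therapy.

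**How treatment was decided.** Treated patients came through the compassionate use programme and were managed on clinicians' judgement (8.1). Section 13.1 states that "patients will not be systematically allocated to treatments".

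**What is recorded.** Section 10.1.7 covers treatments that were prescribed. Section 10.1.5 limits medical history to findings outside the study indication that are also "Considered relevant to the study". The Synopsis and section 10.1.1 list medical history with no such filter. APACHE II, performance status, CRP and pre-treatment IL-6 are listed, if available.

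**What the controls are for.** Section 8.2 says they are there for direct comparison and for efficacy and safety data. Section 11 plans a descriptive comparison within each cohort, and section 11.2.3 rules out statistical comparisons because the sample is small.

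**The concern.** Each treated patient passed a selection step: a physician chose the drug and the programme accepted the patient. A control may have passed no such step. The reasons a patient with ARDS did not receive siltuximab fall into two kinds. Some are close to unrelated to prognosis, such as the drug not being available or the programme not being open. Others are closely tied to it, such as a contraindication, limits on care, or a judgement that the patient did not need the drug. The control definition admits both kinds and the data lists do not separate them.

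At stake is the meaning of the only between-group information the study will produce. The rationale (5.1) and section 8.2 look to it for a view of risk and benefit, and section 11.2.5 allows early release of ad hoc results. The reason for non-treatment cannot be recovered by analysis if it was never collected.

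**Working it through.** The protocol gives no figure for this point to reproduce: section 11.1 says that no sample size estimation was made, and no event rates are given. The check is a reading of the text followed by simple arithmetic on the stated size.

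**1. Is there a candidacy rule for controls?** The relevant places are the Synopsis, 8.1, 8.2, 9.1.1, 9.1.2 and 11.1. Together they require consent, the 9.1 criteria, four match factors and a treatment other than siltuximab. None requires that the control met the programme's criteria, or was considered for or offered the drug. The 48-hour criterion also speaks of being treated, without saying what that means for a control.

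**2. Is the reason for non-treatment recorded?** The relevant places are the Synopsis list and 10.1.1 to 10.1.8. They hold treatments given, history, severity scores, laboratory values and events. None holds a reason for not giving siltuximab.

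**3. What do existing rules already remove?**
- Active non-COVID infection excludes everyone, so a patient passed over for that reason cannot be a control.
- Cohort B controls are in ICU and within 48 hours of starting invasive ventilation, which leaves little room for limits on care. That mechanism matters mainly in Cohort A.
- Age decade and P/F band remove part of any prognostic difference. Comorbidity, APACHE II, CRP, IL-6 and calendar date are not match factors.

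**4. Direction.** If the drug has no effect, and treated patients share the event rate of candidate controls, the spurious difference (control minus treated) is

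f × (p_non-candidate − p_candidate),

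where f is the share of controls who were not candidates. It is positive (favouring siltuximab) if non-candidates were frailer, and negative if they were judged too well.

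**5. Illustration only; every rate here is an assumption.**
- *Frailer non-candidates.* Candidate rate 30–40%, non-candidate rate 60–80%, f 10–50%. Smallest: 0.10 × (0.60 − 0.40) = 2 points. Largest: 0.50 × (0.80 − 0.30) = 25 points.
- *Non-candidates judged too well.* From the same candidate rates the non-candidate rate cannot fall below zero. At f = 50% the spurious difference against siltuximab is at most 0.50 × 0.30 = 15 to 0.50 × 0.40 = 20 points.

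**6. Sensitivity to one control, from the protocol's own numbers.**
- Pairs: 50 / 2 = 25.
- Cohort A: 25 × 0.75 = 18.75, about 19. Cohort B: 25 × 0.25 = 6.25, about 6.
- One control whose outcome changes because of selection moves the control rate by 1/19 = 5.3 points in Cohort A and 1/6 = 16.7 points in Cohort B.

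Fifty is a ceiling, so with fewer pairs these steps are larger. For Cohort B they apply to the mortality part of the primary endpoint, not to length of ICU stay.

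**The case against.** The strongest reply is that this is a small, hypothesis-generating study. Confounding by indication is inherent in such a design, and section 11.2.3 forgoes statistical comparison for that reason. The programme's own criteria are not in the document. If they equal section 9.1, a candidacy sentence changes nothing. A reason assigned in retrospect is itself a judgement that knowledge of outcome could colour, and routine notes may not contain it.

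Much of this stands as a limit on consequence. It does not dispose of the point, because section 8.2 still relies on direct comparison and a descriptive label does not remove bias from a contrast that is published. Even if the programme's criteria equal section 9.1, physicians still chose among eligible patients, so the reason field keeps its value. The worry about retrospective reasons can be met by restricting the source to notes dated at or before the index time.

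A reader might also infer several stronger things that the protocol does not support:
- *That nothing collected would reveal the problem.* APACHE II, performance status, CRP, IL-6 and medical history are listed if available, section 10.1.2 says collection is the same for all patients, and baseline data will be tabulated. Part of an imbalance could show. The reason for non-treatment could not.
- *That comorbidity is recorded only when judged relevant.* Only section 10.1.5 has that filter. The Synopsis and 10.1.1 do not, so the defect is an inconsistency.
- *That whoever completes the form knows the outcome.* The protocol does not say so, and the programme was still enrolling.

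**Conclusion.** The point holds in a limited form. The protocol does not require controls to have been candidates for siltuximab and does not record why they did not receive it. Comorbidity is neither matched on nor consistently specified. The siltuximab-versus-control contrast is therefore open to confounding by indication beyond what age, sex, P/F band and antiviral therapy remove.

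It is tempting to conclude that the bias favours siltuximab. The protocol does not support that: nothing in it says who was passed over, and patients judged too well would push the contrast the other way. Nor does it support any particular size. The only size that follows from its own numbers is the leverage of a single control, about 5 points in Cohort A and 17 in Cohort B. That assumes the full 50 patients, 1:1 matching and the estimated 3:1 split. The 2 to 25 point range, and its counterpart in the other direction, only restate assumed rates.

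This is a cheap improvement that would make the comparison easier to interpret. It does not invalidate a descriptive study.

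**What to change.** 1. **Section 9.1.1.** Add: *Controls must have met the eligibility criteria of the compassionate use programme at the index time (start of NIV/CPAP for Cohort A, start of invasive ventilation for Cohort B).* If those criteria equal section 9.1, the sentence costs nothing.
2. **Case report form, controls only.** Add a field *reason siltuximab not given*: not available / programme not open / refused / contraindicated / not for escalation / judged not necessary / unknown. Take it from notes dated at or before the index time and complete it without reference to outcome. Do not use as controls patients documented as non-candidates. Report the contrast with and without controls whose reason is unknown.
3. **Section 10.1.5.** Replace the relevance filter with a fixed present/absent comorbidity list taken from the admission record for every patient, tabulated by group. This also removes the inconsistency with the Synopsis and section 10.1.1.

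**Cost.** One eligibility sentence and two form items drawn from existing records, with no change to anyone's treatment. The control pool will be smaller, some matches may be harder to find, and some reasons will be unknown.
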